## **6.4. Handling of Dropouts or Missing Data**

Missing data on the primary endpoint, HiSCR response, and other dichotomous endpoints will be imputed as nonresponse. As a supplementary analysis, the primary endpoint at week 16 will be imputed using the last observation prior to missingness. For other endpoints, including continuous secondary endpoints, missing data may be imputed using the last observation prior to missingness or other appropriate imputation methods.

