5.1. Inclusion Criteria

Participants are eligible to be included in the study only if they meet all of the following criteria during the screening period, unless otherwise specified below:

Informed consent

[1] Are capable of giving signed informed consent as described in Appendix 10.1, which includes compliance with the requirements and restrictions listed in the informed consent form (ICF) and in this protocol.

Participant characteristics

[2] Are male or female patients from 18 to 65 years of age (inclusive), at the time of signing the ICF.

Note: Contraceptive use by men or women should be consistent with local regulations regarding the methods of contraception for those participating in clinical studies. Contraception requirements for participants in this study are provided in Appendix 10.4.

HS-related inclusion criteria

- [3] Have a diagnosis of HS for at least 6 months before baseline (the randomization visit).

 Note: a participant with a clinical history of HS may be considered for enrollment if other eligibility criteria are met and if the clinical history is documented by the investigator based on review of the participant's medical history at screening.
- [4] Have HS lesions in at least 2 distinct anatomical regions (for example, right and left axilla; or right axilla and right inguino-crural fold); and at least one of the lesions must be at least Hurley Stage II or Hurley Stage III.
- [5] Have had an inadequate response or intolerance to a 28-day course of oral antibiotics. Examples of inadequate response include the following: any lesion increased in Hurley stage, any lesion requiring intra-lesional steroid injection or incision and drainage, and/or any new anatomic areas developed lesions during the antibiotic course.
- [6] Have a total abscess and inflammatory nodule (AN) count greater than or equal to 4.
- [7] Must agree to use daily, and throughout the duration of the study, one of the following over-the-counter topical antiseptics on body areas affected with HS lesions: chlorhexidine gluconate, triclosan, benzoyl peroxide, or dilute bleach in water.

[8] Are able and willing to comply with the following requirements for use of antibiotics:

If using topical antibiotics for HS at screening, the participant must stop them at least 14 days before baseline (the randomization visit) and must not resume topical antibiotics throughout the duration of the study.

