9.2. Sample Size Determination

Approximately 100 patients will be screened to achieve approximately 63 participants randomized in a 2:1 ratio to one of two treatment groups:

approximately 42 participants randomized to LY3041658, and

approximately 21 participants randomized to placebo.

For all randomized patients, approximately 45 patients are expected to complete the 16 weeks' treatment period. This sample size provides at least 80% power to the primary endpoint of HiSCR response. This calculation is a 2-sided test for superiority of LY3041658 compared to placebo on HiSCR response rate with significance level of 0.05 CCl

CCI

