## 6. A Priori Statistical Methods

### 6.1. Statistical Hypotheses

The study will compare LY3041658 with placebo in adults with HS. The primary study objective is to demonstrate superior efficacy of LY3041658 over placebo.

The primary comparison of interest is the proportion of participants achieving HiSCR response at Week 16.

Secondary comparisons include the mean change of AN count and Skin Pain – HS NRS from baseline to Week 16.

[figure not shown]
Efficacy comparisons will be made without regard to changes to any background therapies. No adjustments for multiplicity will be made across the efficacy assessments. Participants who discontinue the treatment or the study prior to Week 16 will be considered a nonresponder for all relevant analyses.

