### 6.7.3. Exploratory Endpoints

#### 6.7.3.1. Additional HiSCR Response Definitions

The primary endpoint will be assessed using different definitions of HiSCR response at Week 16. Specifically, the needed reduction in AN count will be modified from 50% to 75% and to 90%. The same analysis method used for the primary endpoint will be used for these exploratory analyses. The percentage of responders achieving, HiSCR50, HiSCR75, and HiSCR90, in the mITT and the PPS population will be summarized by visit and by treatment arm to which the patients were randomized at Week 0 (Visit 2). A plot of the percentage of responders over weeks will be provided.

The proportion of visits that a patient achieves HiSCR response out of the total visits the patient attends during study period 1 and 2 (Week 0 to Week 36) will be calculated as follow,

$$\frac{\text{\# of visits the patient achieves HiSCR response}}{\text{Total \# of visits the patient attends}} * 100.$$

The HiSCR response is defined in Section 6.7.1 which is based on a patient's baseline values. The summary statistics of the proportion of visits achieving responses will be summarized by treatment arms to which the patients were randomized at Week 0 (Visit 2).

Moreover, the restricted mean response time (RMRT), a measure of the average time a responder stays a responder within a specified time period, will be provided up for responders at week 16 up (Visit 10) to week 36 (Visit 20) in each treatment arm, respectively. The time to loss of response in HiSCR50 is defined as  $\geq 50\%$  increase in AN compared to the average AN count from the 3 previous visits, and the increase was  $\geq 3$  AN from the average AN count of the 3 previous visits. Specifically, the RMRT is calculated as,

$$\sum_{k=10}^{20} \left\{ \prod_{v=10}^k \left( 1 - \frac{\delta_v}{R_v} \right) \right\} \times 2 \text{ weeks}$$

Where  $\delta_v$  is the number of patients who are responder at Visit 10 (week 16) but first loss response at Visit  $v$  and  $R_v$  is the number of patients who are responder at Visit 10 (week 16) and stay reponse before Visit  $v$ . The average RMRT will be summarized by treatment arm to which the patients were randomized at Week 0 (Visit 2).

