#### 6.7.3.2. Lesion Counts

The mean change from baseline to Week 16 for the total number of abscesses, inflammatory nodules, draining fistulae, and abscess and inflammatory nodule (AN) will be individually summarized and assessed using ANCOVA. Moreover, we will calculate the proportion of patients that achieve 50%, 75% and 90% decreases in AN count at W12 and W16. In addition to AN reduction, the proportion of patients with disease flare will be calculated up to W16, defined as a  $\geq 25\%$  increase in AN count from the baseline and  $\geq 2$  in AN count.

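### The blanket nonresponse imputation in SAP 6.4 has no safe direction for disease flare, where meeting the criterion is bad, and the second flare condition as worded excludes nobody.

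*SAP*

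**What the plan says.** SAP 6.4 sets one rule for every binary endpoint: "Missing data on the primary endpoint, HiSCR response, and other dichotomous endpoints will be imputed as nonresponse". SAP 6.1 adds: "Participants who discontinue the treatment or the study prior to Week 16 will be considered a nonresponder for all relevant analyses". Neither passage mentions flare or says what nonresponse means for an unfavourable event.

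SAP 6.7.3.2, under exploratory endpoints, says "the proportion of patients with disease flare will be calculated up to W16". It defines flare as a rise of at least 25% ("increase in AN count from the baseline and") together with at least 2 in AN count. The word for increase is not repeated in the second part, and the section gives no missing-data rule of its own.

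For loss of response, SAP 6.7.3.1 does say that its second condition is an increase, of at least 3 "AN from the average AN count of the 3 previous visits".

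Protocol 5.1 sets the entry minimum: "Have a total abscess and inflammatory nodule (AN) count greater than or equal to 4".

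**The concern.** For HiSCR, the 50/75/90% AN reductions and the 30% NRS reductions, setting a missing value to criterion not met counts against the participant. For flare the same coding counts in the participant's favour, so one dropout could be a HiSCR failure and flare-free in the same report. Even if 6.4 is not invoked, a derivation that looks for any qualifying count and finds none gives the same answer by default.

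Flare is the one binary worsening measure among the lesion endpoints to Week 16, and people who leave because their disease worsens are not a random subset. If dropout differs between arms, the coding choice can alter which arm looks worse. SAP 6.3.3 assigns categorical efficacy variables to logistic regression with a p-value, so a formal comparison of flare may follow, although 6.7.3.2 says only that the proportion will be calculated.

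The second flare condition looks like a guard against trivial rises in people with few lesions. If it is programmed as a count rather than a change, the guard does nothing.

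**Working it through.** **Inputs from the documents**
- Protocol 9.2: "Approximately 100 patients will be screened to achieve approximately 63 participants randomized in a 2:1 ratio to one of two treatment groups", with about 45 expected to complete 16 weeks. Non-completers: 63 − 45 = 18, and 18/63 = 28.6%.
- SAP 6.2: 51 randomised and the same 45 completers. Non-completers: 51 − 45 = 6, and 6/51 = 11.8%.
- Entry AN count: at least 4 (Protocol 5.1).

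The documents give no flare rate and no dropout by arm. The rates and splits below are assumptions.

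**Step 1: effect on a reported flare rate.** Let *r* be the flare rate in completers, *d* the proportion dropping out, and *s* the share of dropouts with a flare recorded before or at exit. With missing = no flare, the reported rate is *r*(1 − *d*) + *sd*. With missing = flare, it is *r*(1 − *d*) + *d*. Take *r* = 40%, so 0.40 × 45 = 18 completers flare.

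| Dropout | *s* | Missing = no flare | Missing = flare |
|---|---|---|---|
| 18/63 | 0 | 18/63 = 28.6% | 36/63 = 57.1% |
| 18/63 | 25% | 22.5/63 = 35.7% | 57.1% |
| 18/63 | 50% | 27/63 = 42.9% | 57.1% |
| 6/51 | 0 | 18/51 = 35.3% | 24/51 = 47.1% |

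**Step 2: effect on the comparison.** Use the protocol's 42 and 21 per arm, 40% flare among completers in both arms, and no flare recorded in any dropout.
- Equal dropout (12/42 and 6/21): both arms read 28.6% with missing = no flare and 57.1% with missing = flare. The difference is zero under either coding.
- Unequal dropout (6/42 active, 12/21 placebo), missing = no flare: 0.40 × 36/42 = 34.3% against 0.40 × 9/21 = 17.1%.
- Same unequal dropout, missing = flare: (14.4 + 6)/42 = 48.6% against (3.6 + 12)/21 = 74.3%.

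The sign of the difference reverses with the coding: +17.1 points becomes −25.7.

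**Step 3: the second flare condition.** Let *b* be the baseline AN count. The smallest whole-number rise that meets the 25% condition is *b*/4 rounded up.
- *b* = 4: a rise of 1 (to 5).
- *b* = 5 to 8: a rise of 2.
- *b* = 9 to 12: a rise of 3.

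Read as a count of at least 2, the condition is always true: from *b* ≥ 4 the follow-up count is already at least 5. Checking every baseline from 1 to 60 found no case excluded. Read as an increase of at least 2, it excludes only 4 to 5 lesions when *b* ≥ 4. It would also exclude a rise of 1 from a baseline of 1, 2 or 3, which the entry criterion should prevent.

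**The case against.** The strongest counter-argument is that nonresponse can mean treatment failure. For flare, failure is a flare, and then the rule is already conservative. A reader might infer from 6.4 that the SAP declares dropouts flare-free, but the text does not say that. It leaves the direction undefined, and the unfavourable result comes from coding flare as the other binary endpoints are coded. This part of the objection stands, and it limits the point to an unsuitable rule with an undefined direction.

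Second, flare is cumulative. Lesions are counted every 2 weeks to Week 16 and, as far as the broken table in the Schedule of Activities can be read, at the ETV and unscheduled visit V997 as well. Someone who leaves because of worsening may well have a qualifying count already. This also stands: it would be wrong to infer that all 18 of 63 lose their flare status, and the *s* = 0 rows in the working are the extreme. Nothing in SAP 6.7.3.2 excludes ETV or V997 counts. It does not say that they are used.

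Third, coding every discontinuer as flared is not neutral either. It turns stops for pregnancy, liver tests or unblinding into flares, and it pushes the comparison the other way under unequal dropout (Step 2). That is a good reason not to make it the main rule.

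Fourth, an increase of at least 2 is probably what the second condition intends, and the readings differ in a single transition. That is true, but the SAP spells out the increase for loss of response and not here.

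**Conclusion.** The point holds as a defect in an exploratory endpoint. One imputation rule covers all dichotomous endpoints, it does not suit an unfavourable one, and two competent programmers could code flare in opposite directions. Applied as for the other binary endpoints, it lowers the flare rate in the arm that loses more participants.

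At an assumed 40% completer rate, the reported rate would be 28.6% (protocol dropout) or 35.3% (SAP dropout) if no dropout had flared. It would be 35.7% to 42.9% on the protocol numbers if 25% to 50% of dropouts had flared before leaving. The between-arm effect depends on unequal dropout and is nil when dropout and completer flare rates are equal. The sign reversal in Step 2 shows what is possible under an assumed split and does not predict what will happen.

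The second condition is a wording fault. Read literally it does no work; read as an increase it matters only for 4 to 5 lesions. The point should not be taken to cast doubt on HiSCR, where nonresponse imputation is conservative, or on the secondary endpoints.

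**What to change.** - **SAP 6.4:** limit nonresponse imputation to dichotomous endpoints whose criterion is favourable, and refer to 6.7.3.2 for flare.
- **SAP 6.7.3.2, missing data:** derive flare from all lesion counts through the last assessment up to Week 16, naming ETV and V997 as included. State whether post-treatment follow-up counts that fall before Week 16 also enter. Report missing = flare and missing = no flare as sensitivity analyses, by arm, with the number of participants whose status is undetermined.
- **SAP 6.7.3.2, definition:** if that is the intent, define flare as a rise of at least 25% and an absolute increase of at least 2 in AN count, both from baseline.

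The cost is SAP wording, one extra derivation and two sensitivity rows. Data collection, trial conduct and the primary and secondary analyses do not change. The main flare result will still understate flare if participants worsen after their last count, and the two sensitivity rows bound that.

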9.4.1.3. Missing Data Imputation

Missing data on the primary endpoint, HiSCR response, will be imputed as nonresponse. For other endpoints, including continuous secondary endpoints, missing data may be imputed using the last observation prior to missingness or other appropriate imputation methods.

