### **6.3.3. Analysis Methods**

The main analysis of categorical efficacy variables and health outcomes variables will use a logistic regression analysis with treatment group in the model. The p-value and 100(1-alpha)% CI for the odds ratio from the logistic regression model are used for primary statistical inference. The difference in percentages and 100(1-alpha)% CI of the difference in percentages using the Newcombe-Wilson without continuity correction will be reported. The p-value from the Fisher's exact test will also be produced as a secondary analysis.

The main analysis for all continuous efficacy and health outcomes variables will use mixed model repeated measures (MMRM) analysis. The model will include treatment, region, baseline disease severity, visit, and treatment-by-visit-interaction as fixed categorical effects and baseline and baseline-by-visit-interaction as fixed continuous effects. An unstructured (co)variance structure will be used to model the between- and within-patient errors. If this analysis fails to converge, the heterogeneous autoregressive [ARH(1)], followed by the heterogeneous compound symmetry (CSH), followed by the heterogeneous Toeplitz (TOEPH) will be used. The Kenward-Roger method will be used to estimate the degrees of freedom. Type III tests for the least-squares means (LSM) will be used for the statistical comparison. The LSM difference, standard error, p-value and 100(1-alpha)% CI will also be reported.

Fisher's exact test will be used for the adverse events (AEs), discontinuation, and other categorical safety data for between-treatment group comparisons. Continuous vital signs, body weight, and other continuous safety variables, including laboratory variables, will be analyzed by an ANCOVA with treatment group and baseline value in the model. The significance of within-treatment group changes from baseline will be evaluated by testing whether or not the treatment group LSM changes from baseline are different from zero; the standard error for the LSM change will also be displayed. Differences in LSM will be displayed, with the p-value associated with the LSM comparison to placebo and a 95% CI on the LSM difference also provided. In addition to the LSMs for each group, the within-group p-value for the change from baseline will be displayed. Treatment-emergent high/low for categorical laboratory safety analyses will also be produced.

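### For AN count and Skin Pain NRS the plan permits LOCF, names no other imputation method, and leaves it unclear whether a Week 16 ANCOVA or the MMRM governs

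*SAP*

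**What the plan says.** Three parts of the plan bear on the Week 16 analysis of AN count and Skin Pain NRS.

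- **Imputation.** SAP 6.4 states that "missing data may be imputed using the last observation prior to missingness or other appropriate imputation methods". Protocol 9.4.1.3 has the same rule: "For other endpoints, including continuous secondary endpoints, missing data may be imputed using the last observation prior to missingness or other appropriate imputation methods". LOCF is the only method named.
- **Model.** SAP 6.7.2 and protocol 9.4.3 assign both endpoints to ANCOVA of the change to Week 16. SAP 6.7.2 adds a log link for AN count. SAP 6.3.3 says something different: "The main analysis for all continuous efficacy and health outcomes variables will use mixed model repeated measures (MMRM) analysis". It then specifies the model, an unstructured covariance with three named fallbacks, and Kenward-Roger degrees of freedom.
- **Attrition.** Protocol 9.2 expects about 45 of about 63 randomized participants to complete the 16 weeks. SAP 6.2 still has 45 of about 51. The protocol's amendment rationale says that discontinuation has run above expectation.

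Under protocol 7.1.1, a participant who stops study drug has an early termination visit and post-treatment follow-up visits. No Week 16 visit is planned for that participant. Lesion counts and skin pain are scheduled every 2 weeks through Week 16 (protocol 1.3, Table 1).

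**The concern.** A single-time-point ANCOVA needs a Week 16 value. A participant who stops early will usually not have one, so the analyst must either leave that participant out or impute. The only imputation named is to carry the last value forward.

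LOCF fixes each dropout at the improvement reached so far and treats that value as if it had been observed at Week 16. If lesion counts are still changing, the imputed value is systematically short of the Week 16 value, even when dropout has nothing to do with outcome. The error in the treatment difference then depends on how many leave each arm and when, not only on the drug.

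The SAP already contains a model that avoids this. The MMRM uses the observed 2-weekly visits and needs no imputed values. But the text does not settle whether the MMRM or the ANCOVA governs the two secondary endpoints, so the approved SAP leaves both the model and the missing-data method open to choice.

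**Working it through.** **Attrition implied by the documents**

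- Protocol 9.2: 1 − 45/63 = 18/63 = 28.6%. Check: 45/(1 − 0.2857) = 63.
- SAP 6.2: 1 − 45/51 = 6/51 = 11.8%. Check: 45/(1 − 0.1176) = 51.

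Neither percentage is printed. The protocol figure goes with the increased enrollment.

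**Bias of LOCF under random dropout**

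Let d be the fraction without a Week 16 value, g the mean share of the Week 16 change already reached at the last visit, and T the mean Week 16 change common to both arms when the drug has no effect.

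- Equal dropout: LOCF estimate = true difference × [1 − d(1 − g)].
- No drug effect, unequal dropout: size of false difference = (d_active − d_placebo)(1 − g) × T.

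Assumptions, none of them in the documents: the last visit is uniform over Weeks 0–14 or Weeks 2–14; the trajectory is linear, or early (exponential approach with a 4-week time constant, scaled to the Week 16 value); the true difference is −3.0 lesions; T is an improvement of 4 to 6 lesions.

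For the linear case, g = 7/16 = 0.4375 (Weeks 0–14) or 8/16 = 0.5 (Weeks 2–14). For the early case, g = 0.701 or 0.801.

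The unequal split is 15/42 active v 3/21 placebo (18 dropouts in all): 0.357 − 0.143 = 0.214.

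| Trajectory, last visit | 1 − 0.2857(1 − g) | −3.0 estimated as | Shortfall | 0.214(1 − g) | False difference, T = 4 to 6 |
|---|---|---|---|---|---|
| Linear, Weeks 0–14 | 0.839 | −2.52 | 16.1% | 0.121 | 0.48–0.72 |
| Linear, Weeks 2–14 | 0.857 | −2.57 | 14.3% | 0.107 | 0.43–0.64 |
| Early, Weeks 0–14 | 0.915 | −2.74 | 8.5% | 0.064 | 0.26–0.38 |
| Early, Weeks 2–14 | 0.943 | −2.83 | 5.7% | 0.043 | 0.17–0.26 |

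- **Direction.** With 15/42 v 3/21 the false difference goes against the drug. With 9/42 v 9/21 the factor is 0.214 − 0.429 = −0.214, so the size is the same and the false difference favours the drug.
- **At the SAP's attrition.** With d = 0.1176 and equal dropout, the shortfall is 0.1176 × (1 − g), from 2.3% to 6.6%.
- **Skin Pain NRS.** The proportions carry over as a share of the change in any endpoint with the same trajectory shape. No separate calculation was made on the NRS scale.

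**Type I error**

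This was simulated with 20,000 trials per setting: 42 v 21, between-participant SD of 3 lesions in the Week 16 change, residual SD of 2, and a two-sample t test on the LOCF change. With no drug effect and 15/42 v 3/21 dropout, type I error is about 7–9% under the linear trajectory and about 5–6% under early response. With equal dropout it does not exceed 5%.

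**The case against.** Several points on the other side stand.

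- **LOCF is not required.** A reader might infer that the ANCOVA must be filled with LOCF. The wording is permissive and allows other appropriate methods. The defect is an open choice with one named, weak option.
- **MMRM is already in the plan.** If SAP 6.3.3 governs, LOCF is unnecessary for these endpoints. This is true, and it makes the conflict with SAP 6.7.2 and protocol 9.4.3 the root of the problem.
- **The harm depends on assumptions.** Participants who stop drug have an early termination visit that includes lesion counts and skin pain, so a last value at Week 0 should be uncommon. With early response the bias is small. Type I inflation needs unequal dropout, and no document reports dropout by arm. The calculation uses raw change, not the log link of SAP 6.7.2.
- **The 29% is derived.** The SAP's own counts give 12%.

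A reader might also extend the point to the primary endpoint, because SAP 6.4 adds that "As a supplementary analysis, the primary endpoint at week 16 will be imputed using the last observation prior to missingness", while SAP 6.1 counts discontinuers as nonresponders. The documents do not support that extension. SAP 6.4 keeps nonresponse as the main rule: "Missing data on the primary endpoint, HiSCR response, and other dichotomous endpoints will be imputed as nonresponse". The LOCF version is labelled supplementary. Multiple imputation of lesion counts in its place would also classify some discontinuers as responders, so preferring it is a matter of taste.

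**Conclusion.** The concern holds for the two continuous secondary endpoints, and only there. The plan allows LOCF, names no alternative imputation, and gives two incompatible statements of the main model.

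If ANCOVA with LOCF is used at the protocol's implied 29% non-completion, a treatment effect that grows over time is understated by roughly 6–16% under equal random dropout. With the 15/42 v 3/21 split or its reverse and no drug effect, the false difference is about 0.2–0.7 lesions, in a direction set by which arm loses more participants, and type I error is about 5–9%. The upper ends need linear improvement; the lower ends correspond to early response. Trajectory, timing and dropout split are all assumed. If MMRM on observed visits is used, this LOCF bias does not arise.

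This should be corrected, because the better method is already written into the SAP and the protocol reports discontinuation above expectation.

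**What to change.** Reconcile SAP 6.3.3 with SAP 6.7.2 and protocol 9.4.3 by stating that the SAP 6.3.3 MMRM, fitted to the observed 2-weekly visits, is the Week 16 analysis for AN count and Skin Pain NRS. Remove LOCF as an option for these two endpoints in SAP 6.4, and align protocol 9.4.1.3. The supplementary LOCF analysis of HiSCR may stay, labelled as supplementary.

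The change needs no new data or visits, but it has costs:

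- SAP rewording and some programming.
- MMRM relies on data being missing at random.
- With eight post-baseline visits the unstructured covariance has 8 × 9/2 = 36 parameters, to be estimated with about 45 completers. The fallback structures in SAP 6.3.3 may therefore be needed.
- SAP 6.7.2 treats AN count on a log scale and the MMRM as written does not. The SAP must say how that treatment is kept or why it is dropped.
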